6.3.3 Compliance to Product Allocation

Compliance will be ensured by strict distribution of the products (product by product) and collection of used Tobacco Sticks, the CC butts and/or the NNS after each use. This information will be documented in appropriate logs.

In addition, in subjects using NNS, the compliance will be chemically verified using exhaled CO breath. The cut-off point for the CO breath test value to distinguish tobacco use vs. no tobacco use will be 10 ppm (Bennowitz et al, 2002).

Furthermore, the CO breath test will be considered as a measure of compliance during the wash-out days for all subjects.

7 DERIVED AND COMPUTED VARIABLES

Mean change from baseline is the mean of all individual subjects' change from baseline values (baseline is defined in Section 11.1.4 "Definitions for Statistical Data Analysis"). Each individual change from baseline will be calculated by subtracting the individual subject's baseline value from the value at the timepoint. The individual subject's change from baseline values will be used to calculate the mean change from baseline.

Reported BMI will be calculated from the body weight and height using the following formula:

Philip Morris Products S.A.Statistical Analysis PlanConfidentialProtocol ZRHR-PK-01-EUFinal v 3.0 / 08 May 2014Page 19 of 72

BMI = $\frac{\text{weight in kilograms}}{\text{height in meters}^2} \quad (\text{ kg/m}^2)$

The QT interval corrected using Fridericia's formula (QTcF) will be calculated as follows:

$$QTcF = \frac{QT}{\sqrt[3]{60/HR}}$$

The QT interval corrected using Bazett's formula (QTcB) will be calculated as follows:

$$QTcB = \frac{QT}{\sqrt[2]{60/HR}}$$

The geometric coefficient of variation (CV) will be calculated using the following formula:

$$CV = 100\sqrt{e^{\text{var}} - 1}$$

where var = the variance from the log transformed data.

7.1 Pharmacokinetic Parameters

The following PK parameters will be determined from the plasma concentration-time profiles of nicotine using non-compartmental procedures in WinNonlin Phoenix, Version 6.2.1, or higher:

Philip Morris Products S.A. Protocol ZRHR-PK-01-EU Statistical Analysis Plan Final v 3.0 / 08 May 2014 Confidential Page 20 of 72

Table 3: Definition of PK Parameters

Parameter	Definition
AUC _(0-last)	Area under the plasma concentration-time curve from start of product
	use to the time of the last quantifiable concentration.
AUC _(0-t')	Area under the plasma concentration-time curve from start of product
	use to the subject-specific time (t') of maximum nicotine concentration
	following single use of the CC or NNS product, between the THS 2.2
	and CC, as well as the THS 2.2 and NNS.
AUC _(0-∞)	Area under the plasma concentration-time curve from start of product
(-)	use extrapolated to infinite time.
%AUC _{extrap}	Percentage of AUC that is extrapolated from t _{last} to infinity.
C _{max}	Maximum observed plasma concentration.
Clast	Last quantifiable concentration.
t _{last}	Time of the last quantifiable concentration.
t _{max}	Time of maximum observed plasma concentration.
λz	Terminal elimination rate constant, estimated by linear regression
	analysis of the natural log-transformed concentration-time data.
t _{1/2}	Terminal elimination half-life.

Additional PK parameters may be determined in order to support the interpretation where appropriate.

The actual blood sampling times post-exposure collected in the eCRF will be used in the computation of the PK parameters, with the exception of pre-exposure (-15 mins) blood sampling time which will be considered as time zero (T_0).

7.1.1 Calculation of C_{max} and t_{max}

The minimum requirement for the determination of the C_{max} is the inclusion of at least one quantifiable concentration within 1 hour post-exposure.

 C_{max} and t_{max} will be obtained directly from the plasma concentration-time profiles. If C_{max} occurs at more than one time point, t_{max} will be assigned to the first occurrence of the C_{max} .

7.1.2 Calculation of AUC

The minimum requirement for the calculation of the AUC is the inclusion of at least 3 consecutive plasma concentrations above the lower limit of quantification (LLOQ), with at least 1 of these concentrations following C_{max} .

 $AUC_{(0-last)}$ and $AUC_{(0-t')}$ will be calculated using the linear trapezoidal method.

 $AUC_{(0-t')}$ will be calculated automatically by linear interpolation within WinNonlin, where t' is the subject-specific actual time of maximum nicotine concentration following single

Philip Morris Products S.A. Protocol ZRHR-PK-01-EU Statistical Analysis Plan Final v 3.0 / 08 May 2014 Confidential Page 21 of 72

use of the CC or NNS product, between the THS 2.2 and CC, as well as the THS 2.2 and NNS.

 $AUC_{(0-\infty)}$ will be calculated as follows:

$$AUC_{0-\infty} = AUC_{0-last} + \left(\frac{C_{last}}{\lambda_z}\right)$$

Where C_{last} is the last quantifiable concentration and λ_z is the terminal elimination rate constant.

%AUC_{extrap}, the percentage of AUC_{$(0-\infty)$} extrapolated beyond t_{last}, will be calculated according to the following formula:

$$\% AUC_{extrap} = \left(1 - \frac{AUC_{0-last}}{AUC_{0-\infty}}\right) \ge 100$$

 $AUC_{(0-\infty)}$ values where the percentage extrapolation is greater than 20% will be flagged in the data listings and will be reviewed for inclusion in the analysis during the pre-analysis data review.

7.1.3 Criteria for Calculating the Apparent Terminal Elimination Half-Life

 $t_{1/2}$ will be calculated according to the following formula:

$$t_{\frac{1}{2}} = \frac{\ln(2)}{\lambda_z}$$

where λ_z will be calculated by least squares (LS) linear regression of the terminal portion of the log-transformed plasma concentration-time curve.

The start of the terminal elimination phase for each subject will be defined by visual inspection and will be the first point at which there is no systematic deviation from the log-linear decline in plasma concentrations. The concentrations included in the terminal elimination phase will be flagged in the data listings.

Period of Estimation

- Apparent terminal (elimination) half-lives will be calculated, where possible, over at least 2 half-lives. Where an apparent terminal half-life is estimated over less than 2 half-lives, it will be flagged in the data listings.
- An apparent terminal half-life will not be reported if it can only be calculated over a period that is less than 1.5 half-lives.

Philip Morris Products S.A. Protocol ZRHR-PK-01-EU Statistical Analysis Plan Final v 3.0 / 08 May 2014 Confidential Page 22 of 72

Number of Data Points

• At least 3 data points with nicotine concentration greater than the LLOQ will be used for each subject in the regression analysis. An apparent terminal half-life will not be reported if derived from less than 3 data points.

Goodness of Fit

- When assessing apparent terminal phases, the coefficient of determination, R² adjusted value, will be used as a measure of the goodness of fit of the data points to the determined line. This parameter will be used as it is considered to be a better assessment of the goodness of fit, compared to R², as it adjusts for the number of points included in the line therefore allowing for a more direct comparison between elimination phases determined using different numbers of data points.
- Apparent terminal half-life will only be calculated if the R^2 adjusted value of the regression line is greater than or equal to 0.7.

7.1.4 Anomalous Values

If a concentration value is considered to be anomalous due to being inconsistent with the expected PK profile it will be flagged in the listings and will be reviewed for inclusion in the analysis during the pre-analysis data review.

7.2 Biomarkers

7.2.1 CYP2A6

CYP2A6 activity is calculated in plasma as the metabolic ratio of trans-3' hydroxycotinine and cotinine, both expressed in molar equivalent (nmol/L) (Jacob et al, 2011):

$$CYP2A6 = \frac{HCOT[ng/mL] \times 5.202}{COT[ng/mL] \times 5.675}.$$

Any values below the LLOQ or above the upper limit of quantification (ULOQ) in the component parameters will not be imputed and the derived variable will be set to missing.

The conversion factor will be applied as follows:

Cotinine	The molecular weight is 176.2178 g/mol (Chemical Information
(COT)	Specialized Information Services RN:486-56-6) Therefore to
	transform COT from ng/mL to nmol/L, the result in ng/mL will be
	multiplied by 5.675
Trans-	The molecular weight is 192.217 g/mol (Chemical Information
3'hydroxycotine	Specialized Information Services RN:34834-67-8) Therefore to
(HCOT)	transform HCOT from ng/mL to nmol/L, the result in ng/mL is
	multiplied by 5.202

Philip Morris Products S.A.	Statistical Analysis Plan	Confidential
Protocol ZRHR-PK-01-EU	Final v 3.0 / 08 May 2014	Page 23 of 72

The converted results will be reported to three decimal places and the ratio will be reported as a percentage to two decimal places.

7.3 Questionnaires

7.3.1 Socio-Economic Status Questionnaire

On Day 2, subjects will fill a questionnaire, which will allow the assignment of the subject household's socio-economic status (SES).

The social grading classification (Table 4) that will be used to determine the subject household's SES is based upon the occupation and employment status of the Chief Income Earner (Market Research Society, 2010). Based on the answers of the subjects, data will be recoded in order to assign the head of the household to one of the following socio-economic classes by means of expert judgment based on Market Research Society recommendations (Market Research Society, 2010):

Grade	Social Classes
A	Upper middle class
В	Middle class
C1	Lower middle class
C2	Skilled working class
D	Working class
Е	Those at the lowest levels of subsistence

Table 4: Social Grading Classification

Overall middle class grading will be calculated by adding together grades A, B and C1. An overall working class grading will be calculated by adding together grades C2, D and E. For the derivation of the overall grading there will be no imputation for missing values therefore if one of the individual components is missing then the overall grading will be set to missing.

7.3.2 Fagerström Test for Nicotine Dependence

The FTND will be used in its revised version (Heatherton et al, 1991). These questions are to be answered by the subject themselves. It is conducted at Screening only to determine subject's dependence on nicotine.

Table 5 describes the six questions the questionnaire consists of, and the scores associated with each question.

The FTND total score will be derived by summing the individual item scores if all items are non-missing, otherwise the total score will be set to missing.

Philip Morris Products S.A. Protocol ZRHR-PK-01-EU Statistical Analysis Plan Final v 3.0 / 08 May 2014 Confidential Page 24 of 72

For the FTND total score, descriptive statistics and frequency tables according to the following classification will be provided (Fagerström et al, 2012):

- Mild 0-3
- Moderate 4 6
- Severe 7 10

Table 5: Scoring for the Fagerstrom Test for Nicotine Dependence

	FTND Question	Response	Score
1	How soon after you wake up do you smoke your first cigarette?	 Within 5 minutes 6 to 30 minutes 31 to 60 minutes After 60 minutes 	3 2 1 0
2	Do you find it difficult to refrain from smoking in places where it is forbidden?	YesNo	1 0
3	Which cigarette would you hate most to give up?	The first one in the morningAny other	1 0
4	How many cigarettes per day do you typically smoke?	 10 or less (up to ½ pack) 11 to 20 (a little more than ½ pack, up to a full pack) 21 to 30 (a little more than a pack, up to 1½ packs) 	0 1 2
5	Do you smoke more frequently during the first hours after waking than during the rest of the day?	 31 or more (more than 1½ packs) Yes No 	3 1 0
6	Do you smoke if you are so ill that you are in bed most of the day?	YesNo	1 0

7.3.3 Questionnaire of Smoking Urges Brief

The QSU-brief (**Cox et al, 2001**). is a self-reported questionnaire completed 10 times at the following timepoints at Day 1 and Day 3:

- The first assessment will be done 15 min prior to T_0
- All other assessments will be done after T_0 , at T_0+15 minutes, T_0+30 minutes, T_0+45 minutes, T_0+1 hour, T_0+2 hours (with an allowed time window of +5 min each) and T_0+4 hours, T_0+6 hours, T_0+9 hours, T_0+12 hours (with an allowed time window of +10 min each).

Philip Morris Products S.A. Protocol ZRHR-PK-01-EU Statistical Analysis Plan Final v 3.0 / 08 May 2014 Confidential Page 25 of 72

The QSU-brief consists of 10 items as presented in Table 6.

Table 6: Questionnaire of Smoking Urges Brief - Questions and Factors

	Question	Factor
1	I have a desire for a cigarette right now	1
2	Nothing would be better than smoking a cigarette right now	2
3	If it were possible, I probably would smoke now	1
4	I could control things better right now if I could smoke	2
5	All I want right now is a cigarette	2
6	I have an urge for a cigarette	1
7	A cigarette would taste good now	1
8	I would do almost anything for a cigarette now	2
9	Smoking would make me less depressed	2
10	I am going to smoke as soon as possible	1

All items will be rated on a 7-point scale, ranging from 1 (strongly disagree) to 7 (strongly agree). Higher scores indicate a higher urge to smoke.

Two factor scores and a total score will be derived (**Cox et al, 2001**). Each factor is a subset that includes 5 of the 10 questions as defined in Table 6. Factor 1 represents the desire and intention to smoke with smoking perceived as rewarding, while Factor 2 represents an anticipation of relief from negative effect with an urgent desire to smoke.

The factors and total scores will be calculated by averaging non-missing item scores if at least 50% are non-missing, otherwise the factor or total score will be set to missing.

7.3.4 Modified Cigarette Evaluation Questionnaire

The MCEQ (**Cappelleri et al, 2007**) will be completed by the subject him/herself at Day 1 and Day 3, during CC and THS 2.2 (product use only) to assess the degree to which subjects experience the reinforcing effects of smoking.

Philip Morris Products S.A. Protocol ZRHR-PK-01-EU Statistical Analysis Plan Final v 3.0 / 08 May 2014 Confidential Page 26 of 72

The MCEQ consists of 12 items as presented in Table 7.

Table 7: Modified Cigarette Evaluation Questionnaire - Questions and
Subscales

	Question	Subscale
1	Was smoking satisfying?	Smoking Satisfaction
2	Did cigarettes taste good?	Smoking Satisfaction
3	Did you enjoy the sensation in your throat and chest?	Enjoyment of Respiratory Tract Sensations
4	Did smoking calm you down?	Psychological Reward
5	Did smoking make you feel more aware?	Psychological Reward
6	Did smoking make you feel less irritable?	Psychological Reward
7	Did smoking help you concentrate?	Psychological Reward
8	Did smoking reduce your hunger for food?	Psychological Reward
9	Did smoking make you dizzy?	Aversion
10	Did smoking make you nauseous?	Aversion
11	Did smoking immediately relieve your craving for a cigarette?	Craving Reduction
12	Did you enjoy smoking?	Smoking Satisfaction

Items are assessed on a 7-point scale, ranging from 1 (not at all) to 7 (extremely). Higher scores indicate greater intensity on that scale.

The subscales scores will be derived by averaging the individual non-missing item scores if at least 50% are non-missing, otherwise the subscale score will be set to missing.

7.3.5 Cough Assessment

Subjects will be asked if they have experienced a regular need to cough (e.g., coughing several times) in the last 24 hours prior to assessment. If the answer is 'yes', they will be asked to complete a visual analogue scale (VAS), three Likert scale questions and an open question assessing their cough during previous 24 hours. Assessments will be done on a daily basis from Day 0 to Day 4.

The VAS will assess how bothersome cough is to the subject ranging from 'not bothering me at all' to 'extremely bothersome', and this will be given a numeric value between 0 and 100.

Philip Morris Products S.A. Protocol ZRHR-PK-01-EU Statistical Analysis Plan Final v 3.0 / 08 May 2014 Confidential Page 27 of 72

Subjects will also be asked to assess the intensity and frequency of cough and the amount of sputum production on Likert scales as presented in Table 8

Table 8: Cough Assessment Likert Scales

	Question	Likert Scale
1	The intensity of cough	1 = very mild
		2 = mild
		3 = moderate
		4 = severe
		5 = very severe
2	The frequency of cough	1 = rarely
		2 = sometimes
		3 = fairly often
		4 = often
		5 = almost always
3	The amount of sputum production	0 = no sputum
		1 = a moderate amount of sputum;
		2 = a larger amount of sputum;
		3 = a very large amount of sputum.

7.4 Categorical Variables

Table 9: Categorical Variable Definitions

Variable	Categories	
BMI (kg/m²)	Underweight: Normal range: Overweight: Obese:	< 18.5 ¹ ≥ 18.5 and < 25.0 ≥ 25.0 and < 30.0 ≥ 30.0
FTND total score	Mild: Moderate: Severe:	0 - 3 4 - 6 7 - 10
ISO nicotine level (mg)	≤ 0.6 >0.6 - 1 mg > 1.0 ¹	
ISO tar yields (mg)	1-5 6-8 9-10 >10 ¹	
Daily CC consumption (cig/day)	<10 ¹ 10-19 >19	
CO breath test level (ppm)	≤ 10 > 10	
COHb level	≤ 2% > 2%	

Philip Morris Products S.A. Protocol ZRHR-PK-01-EU Statistical Analysis Plan Final v 3.0 / 08 May 2014 Confidential Page 28 of 72

Variable	Categories
SES (Individual categories)	A Upper middle class
-	B Middle class
	C1 Lower middle class
	C2 Skilled working class
	D Working class
	E Those at the lowest levels of
	subsistence
SES (Overall categories)	Overall middle class
	Overall working class
Adverse event severity	Mild
	Moderate
	Severe
Adverse event relationship	Related
	Not related
Adverse event expectedness	No
·	Yes
Action taken due to adverse event	Discontinuation from study
	Related to product use (if any of the
	following applies: interrupted, stopped,
	or reduced)
	Treatment given (yes/no)
	Other action taken
Outcome of adverse event	Death related to adverse event
	Not recovered or not resolved
	Recovered or resolved
	Recovered or resolved with sequelae
	Recovering or resolving
	Unknown
Seriousness Criteria	Fatal
	Life-threatening
	Requires hospitalization
	Results in disability/incapacity
	Congenital anomaly/birth defect
Severity of device event	Major
-	Minor

Table 9: Categorical Variable Definitions

Note that due to inclusion criteria for the study there should not be any subjects underweight, or reporting <10 cig/day or with ISO nicotine level > 1.0 mg, or ISO tar yields > 10 mg; therefore these categories will not be presented unless there is at least one response.

8 SAMPLE SIZE JUSTIFICATION

A total of 62 smokers will be randomized. This sample size is the sum of the sample size requirements for the THS2.2:CC comparison and the THS2.2:NNS comparison (as described in detail below).

Philip Morris Products S.A. Protocol ZRHR-PK-01-EU

Statistical Analysis Plan Final v 3.0 / 08 May 2014 Confidential Page 29 of 72

A total of 44 subjects are needed to estimate the mean C_{max} parameter ratio between THS 2.2 and CC with a 90% probability of obtaining a margin of error (95% CI) of at most ±20%, assuming that THS 2.2 have a nicotine PK profile similar to CC (C_{max} ratio equal to 1.00) and a 10% dropout rate.

A total of 18 subjects are needed to estimate the mean C_{max} parameter ratio between THS 2.2 and NNS with a precision allowing for the lower bound of the 95% CI exceeding 1.00, with 90% power and assuming a 10% dropout rate. The anticipated geometrical C_{max} ratio between THS 2.2 and NNS is 1.55, based on data reported by **Gourlay and Benowitz**, 1997, and Johansson et al, 1991.

The estimates for the within-subject CV for nicotine C_{max} (36%) and AUC_(0-last) (21%) are based on the data collected in the ZRHX-PK-02 clinical study (**PMI**, 2012a) comparing the nicotine PK profiles of THS 2.1, the predecessor of THS 2.2 and CC. In the absence of data comparing THS and NNS, the same CVs were assumed for the calculation of the sample size related to the THS 2.2:NNS comparison.

Sample size calculations were conducted using SAS version 9.2 for the 95% CI of the mean differences between paired observations (proc power onesamplemeans) in the natural log scale (Senn, 2002). The SAS implementation of the method published by (Beal, 1989) was adopted to estimate the probability of obtaining at most the target confidence interval of $\pm 20\%$.

9 CHANGES FROM THE PROTOCOL SPECIFIED STATISTICAL ANALYSIS

Safety analyses will not be performed by product. Due to the study design it was determined that this presentation is not clear because of the product test at Admission and the selection of arbitrary time points for defining periods associated to the different study products may be misleading. In addition, the safety laboratory evaluations will only be collected prior to any product use and following the use of both products.

Shift tables for safety endpoints will not be produced for this study, because the relevant information will be provided in listings.

Statistical analysis for blood COHb (%) and exhaled CO (ppm) measurements and the QSU-brief questionnaire data will be performed including interaction terms for product and time point to enable LS means to be calculated at each time point in order to explore the pattern of the THS 2.2 effect over time. The main comparison between products will be the comparison over all time points.

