6 INVESTIGATIONAL PLAN

6.1 Study Design

This is a randomized, controlled, 2-period, 4-sequence, single use crossover study. An incomplete block design has been adopted, where each subject will receive two of the three products (Figure 1):

- THS 2.2.
- CC.

Philip Morris Products S.A. Protocol ZRHR-PK-01-EU

Statistical Analysis Plan Final v 3.0 / 08 May 2014 Confidential Page 14 of 72

• NNS.

In total, 62 eligible, healthy smoking subjects will be randomized into one of the 4 sequences in Table 1:

Table 1 Definition	of Randomization	Groups and Sequences
		eroups and bequences

Group	Allocation Ratio	Sequence	Sample Size
•	0.0	1. THS 2.2 then CC	22
Group-1 = THS 2.2 vs. CC	2:2	2. CC then THS 2.2	22
	4.4	3. THS 2.2 then NNS	9
Group-2 = THS 2.2 vs. NNS	1:1	4. NNS then THS 2.2	9

A Screening Visit will be conducted within 4 weeks prior to Admission to the investigational site (Day -29 to Day -2). A demonstration of the THS 2.2 product and the NNS will also be done by the site staff during the screening visit. Subjects will be admitted to the clinic on Day -1 (Admission). On Day -1, as the last procedure of the eligibility assessments on that day, all subjects will undergo a product test prior to enrolment, first THS 2.2 (using up to three Tobacco Sticks) and subsequently the NNS (1 spray of 0.5 mg per nostril as per label). In female subjects, the urine pregnancy test must be negative before the product test is performed with either THS 2.2 or NNS. After all inclusion and exclusion criteria have been satisfactorily met, only subjects willing and ready to use both the THS 2.2 and NNS products can be enrolled. Screening procedures do not necessarily have to be conducted on the same day.

Subjects are enrolled on Day -1, but not randomized until the Day 0 washout, therefore it is possible to have enrolled subjects who do not get randomized.

[figure not shown]
Subjects will be discharged from the investigational site in the morning of Day 4 after all safety examinations of the Day of Discharge have been conducted. After Discharge, subjects will enter into a 7-day safety follow-up to capture spontaneously reported new AEs/SAEs and for active follow-up of ongoing AEs/SAEs. Any AE will in general be followed up until resolved, stabilized i.e., no worsening of the event, or until a plausible explanation for the event has been found.

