6.1.1 Timing of Confinement Period

The 6 day confinement period consists of:

- The Admission Day from admission on site until 06:30 AM on Day 0.
- The first washout period: from 06:30 AM on Day 0 until the time of first product use (T₀) in the time window 6:00 AM-9:00 AM of Day 1.
- The first product exposure period (1 day): starting from T₀ on Day 1, ending 24 hours after T₀.
- The second washout period: from the end of the first product exposure (24 hours after T_0 on Day 1) on Day 2 until the time of product use in the time window 6:00 AM-9:00 AM on Day 3.
- The second product exposure period (1 day): starting from T_0 on Day 3, ending 24 hours after T_0 .
- The discharge procedures from 24 hours after T₀ of the second product use until the time of discharge on Day 4.

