11.6.4.2 Adverse Events

A general summary table of AEs will be presented by sequence and overall, including:

- The number of events and the number and percentage of subjects reporting at least one AE.
- The number of events and the number and percentage of subjects reporting at least one study product –related AE, broken down by product relatedness (related to THS 2.2 / CC, related to NNS) and expectedness (expected, not expected).
- The number of events and the number and percentage of subjects reporting at least one AE broken down by severity, including a subject once with worst severity.

Philip Morris Products S.A. Protocol ZRHR-PK-01-EU Statistical Analysis Plan Final v 3.0 / 08 May 2014 Confidential Page 55 of 72

- The number of events and the number and percentage of subjects reporting at least one AE leading to any action taken, broken down by action taken related to the product (combining the following items: product use interrupted, product use reduced, product use stopped), treatment given (yes, no), study discontinuation, other action taken.
- The number of events and the number and percentage of subjects reporting at least one AE related to study procedure.

Additional summary tables of AEs will be presented by sequence and overall, with a breakdown of the number of events, as well as the number and percentage of subjects reporting each AE, categorized by SOC and PT coded according to the MedDRA dictionary (version 16.0):

- The number of events and the number and percentage of subjects reporting at least one AE.
- The number of events and the number and percentage of subjects with at least one AE related to product exposure and expectedness for investigational product (IP; THS 2.2 or CC) and reference point product (NNS).
- The number of events and the number and percentage of subjects with at least one AE leading to study discontinuation.
- The number of events and the number and percentage of subjects with at least one AE related to study procedure.
- The number of events and the number and percentage of subjects with at least one AE by severity (mild, moderate, severe)

If a subject has more than one occurrence of the same AE, the subject will be counted only once within a PT for each sequence, with the worst occurrence based on the presentation (e.g., for presentation by severity = most severe, for presentation by relationship = most related). Missing information on the intensity of AE will be counted as severe.

TFL number	Title

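### The planned adverse-event tables cannot separate THS 2.2 from conventional cigarettes in Group-1, although the SAP already defines windows that could

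*SAP*

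**What the plan says.** SAP Section 9 records a change from the protocol's analysis: "Safety analyses will not be performed by product". It gives three reasons. The product test at Admission makes such a presentation unclear; "the selection of arbitrary time points for defining periods associated to the different study products may be misleading"; and "the safety laboratory evaluations will only be collected prior to any product use and following the use of both products".

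Section 11.6.4.2 carries this through: "A general summary table of AEs will be presented by sequence and overall, including" the counts by relatedness, severity, action taken and study procedure. The tables by system organ class and preferred term have the same columns, as do the summaries of serious AEs (Section 11.6.4.2.1) and of AEs leading to withdrawal (Section 11.6.4.2.2). Relatedness in the general table is "broken down by product relatedness (related to THS 2.2 / CC, related to NNS"). The detailed tables use "expectedness for investigational product (IP; THS 2.2 or CC) and reference point product (NNS").

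Three other places matter:
- Section 6.1, Table 1: sequence "1. THS 2.2 then CC" has 22 subjects, and the reverse order has 22.
- Section 6.1.1: "The first product exposure period (1 day): starting from" T0 on Day 1 and lasting 24 hours, with the same definition for the second period on Day 3.
- Section 10: the product actually used on each single-use day is derived from the recorded time of first puff, lighting or first spray.

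**The concern.** AE incidence is the first endpoint under the safety objective (Section 5.2, objective 8), and THS 2.2 is the new product. In a crossover, a sequence column says in what order products were used, not which one preceded an event. If relatedness also merges the new product with its main comparator, a reader of the AE tables cannot tell whether events cluster after THS 2.2 or after CC. The data needed to show this appear to be collected already, so the loss would come from the layout of the tables.

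**Working it through.** The plan gives no figure to reproduce on this point. The check is of table layouts, followed by a short illustration.

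**1. Which safety tables can separate THS 2.2 from CC in Group-1?**

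| Output (SAP section) | Split by | Separable? |
|---|---|---|
| AEs, serious AEs, AEs leading to withdrawal (11.6.4.2 to 11.6.4.2.2) | sequence, overall | No |
| Laboratory, spirometry, physical examination (11.6.4.4, 11.6.4.5.4, 11.6.4.5.2) | sequence, baseline and discharge (physical examination also Screening) | No, because of when data are collected |
| Vital signs (11.6.4.5.3) | sequence, study day | Descriptively |
| ECG (11.6.4.5.5) | sequence, Day 1 and Day 3 | Descriptively; the SAP does not say whether the ECG precedes product use |
| Cough (11.6.4.5.6) | sequence, day | Descriptively |

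In the last three rows the sequence and day together identify the product. AEs are the only outcome with onset information that is not shown by day or period.

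**2. Does relatedness help?** Not for this comparison. THS 2.2 and CC form one class and NNS the other.

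**3. Illustration.** Let a and b be the chances of at least one AE after the first and second product. Assume independence, no period effect and no events outside the exposure windows. A sequence then shows

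1 − (1 − a)(1 − b),

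which is unchanged when a and b are swapped. The risks below are assumed; the SAP gives none.

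- THS 2.2 5%, CC 20%: 1 − 0.95 × 0.80 = 0.24.
- THS 2.2 20%, CC 5%: 1 − 0.80 × 0.95 = 0.24.
- Equal risks: 1 − √0.76 = 0.128 each gives 1 − 0.872 × 0.872 = 0.24.

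All three cases give 0.24 × 22 = 5.3 expected subjects with an AE in each Group-1 sequence. Tabulated by product over the 44 randomised subjects, the first case gives 0.05 × 44 = 2.2 after THS 2.2 and 0.20 × 44 = 8.8 after CC. The second case reverses these, and the third gives 0.128 × 44 = 5.6 for each.

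**4. The reasons in Section 9, applied to AEs.**
- Arbitrary time points: Section 6.1.1 already has a window of T0 to T0 + 24 hours, identical for both periods, and Section 10 names the product used in it.
- Product test: it takes place on Day -1, before a wash-out of at least 24 hours (Section 6.1). Its events can be shown as a period of their own.
- Laboratory timing: this concerns samples taken before any product and after both. It does not apply to events with an onset.

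**The case against.** The best case for the plan is that this is a declared and reasoned change. The objective is to monitor safety, and Section 5.4.1 states no safety hypothesis. On Day -1 every enrolled subject tests THS 2.2 and then NNS, and Section 11.4 says smoking is ad libitum that day, so nobody reaches Day 1 unexposed. Section 6.1.1 sets the confinement timetable; it is not an attribution rule for AEs. All AEs are listed, and listings are by default ordered by product as well as sequence (Section 11.1), so nothing is lost from the record.

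Much of this stands. No stated objective goes unanswered, and assigning every event to a product would be misleading. A table that gave everything from Day 1 T0 to Day 3 T0 (about 48 hours) to the first product, and everything from Day 3 T0 to the end of follow-up (up to Day 11) to the second, would recreate the arbitrariness that Section 9 warns of. These arguments do not rule out a table limited to the SAP's own equal 24-hour windows with all other time unattributed. Listings do not replace a summary of incidence.

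A reader might infer more than the document supports:
- That no planned safety table distinguishes THS 2.2 from CC. The vital signs, ECG and cough tables do so descriptively.
- That the AE summaries would look alike whichever product caused the events. NNS relatedness is a separate class, and in the Group-2 sequences, where CC is not randomised, the pooled class mainly reflects THS 2.2.
- That 62, 44 and 18 subjects are exposed to THS 2.2, CC and NNS. Those counts cover the randomised single-use days only and leave out the Day -1 test.

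**Conclusion.** The point holds for the AE, serious-AE and withdrawal tables and for THS 2.2 against CC in Group-1. As laid out, these tables cannot distinguish incidence after one product from incidence after the other, and the reasons in Section 9 do not require that for AEs. It is a weakness of descriptive reporting. The primary analysis and every inferential claim are untouched.

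The layout finding needs no assumption. The 24% figure rests on assumed risks, independence, no period effect and no events outside the windows, and shows only that the by-sequence rate is symmetric in the two products. The remedy assumes that AE onset is recorded finely enough to place an event before or after T0. The SAP does not state that onset times are collected, but its exposure-emergent definition (Section 11.6.4.1) already needs the order of onset and first product use. With at most 44 subjects on both products, the added table would be descriptive only.

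**What to change.** Keep the by-sequence tables. Add one descriptive AE table by onset period, using windows the SAP already has:

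1. Day -1 product test to Day 1 T0, shown as a pre-period and not attributed to a randomised product.
2. T0 to T0 + 24 hours on Day 1 and Day 3, by the product actually used under Section 10. The denominator is subjects exposed to that product on the single-use day. Group-1 is shown apart from Group-2, so that THS 2.2 and CC are read in the same subjects.
3. The second wash-out, and follow-up after the Day 3 exposure period, as separate unattributed rows.

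Footnote that subjects also tested THS 2.2 and NNS on Day -1, that late-onset events are not attributed, and how incomplete onset times were placed. Amend the sentence in Section 9 to match. Splitting THS 2.2 from CC in the relatedness rows would also help if the eCRF records them separately. The SAP does not say, and the table above does not depend on it.

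The cost is one extra table with its footnotes. It needs no new data if AE onset times are held, and no inferential claim changes.
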